## Network-Level Effects of Nitrous Oxide in the Human Brain

### BACKGROUND

General anesthetics can, in coarse terms, be mechanistically classified as “GABAergic” and “non-GABAergic.” Clearly there is great diversity among GABAergic anesthetics such as propofol and the halogenated ethers. However, in general these drugs tend to be potent hypnotics and weak analgesics that are associated with a slow-wave EEG pattern at concentrations consistent with surgical anesthesia. For nitrous oxide, the GABA receptor is not the primary therapeutic target; this drug is a relatively weak hypnotic and potent analgesic that activates higher-frequency activity of the EEG. *Despite these differences, nitrous oxide is pharmacologically classified and clinically used as general anesthetics, alongside propofol and the halogenated ethers.* The study of anesthetic mechanisms will simply not be complete without a neuroscientific understanding of these drugs and the use of fMRI and EEG is the best technology available for systematic human studies. Identifying common neural principles of the anesthetic action of nitrous oxide and GABAergic drugs would be a major advance for the field of anesthesiology that would, for the first time, establish a common and *empirically-demonstrated* neurobiology of anesthetic-induced unconsciousness. This has not been possible with prior molecular or neurophysiological approaches, which motivates our focus on network-level properties.

Of further clinical and scientific interest, nitrous oxide disrupts pain processing at subanesthetic doses. Over the past two decades there has been increased excitement about techniques that probe the functional, structural, and molecular mechanisms involved in human pain and its amelioration.

However, less attention has been focused on how brain networks mediate pain and, moreover, how these same networks are modulated by centrally-acting analgesics such as nitrous oxide. We propose that the dose-dependent analgesic and anesthetic actions of these drugs can be understood as emergent network properties. The hypotheses motivating the currently proposed studies are summarized in the *figure on the right.*

Data derived from chronic centralized pain states suggest that pain occurs when particular brain regions functionally connect with other networks of the brain. Our recent work in fibromyalgia patients has found that the insula, a key higher-order sensory structure, is hyperconnected to the brain’s Default Mode Network (DMN), a constellation of brain regions involved in self-referential thinking (when an individual is not actively engaged with their external environment). Importantly, this enhanced connectivity is associated with self-reports of clinical pain intensity, and successful pharmacologic

treatment is associated with alternative network connectivity patterns (see preliminary data). Therefore, like consciousness and anesthesia, pain and analgesia can be understood by examining brain networks and their alterations.

Relevant Literature: The relevant literature for this study pertains to the brain mechanisms for both analgesic and anesthetic doses of nitrous oxide.

There is one neuroimaging study that address the analgesic role of nitrous oxide (Gyulai et al). In this study, the authors sought to identify the regions of the brain associated with the antinociceptive effects of nitrous oxide to a noxious heat stimulus. Measuring cerebral blood flow, Gyulai et al found that heat stimulus increased cerebral activation of the thalamus, anterior cingulate and supplementary motor area. Although nitrous oxide increased activation of subregions of the prefrontal cortex, nitrous oxide administered while the heat stimulus was applied reduced activation in the thalamus and supplementary motor area. As this study speaks to the analgesic effects of nitrous oxide, it does not measure the brain network properties of nitrous oxide administration at the anesthetic dose.

Preliminary Studies: We have shown previously that fibromyalgia patients display increased resting state connectivity between pain regions such as the insula and other non-pain related areas such as the DMN. Moreover, reductions in this connectivity were associated with reductions in clinical pain: the degree of this connectivity was directly correlated with clinical pain ratings. In our *Anesthesiology* article, we examined the effect of pregabalin, an efficacious analgesic, on chronic clinical pain in fibromyalgia. Prior to and following each treatment period (drug/placebo), patients underwent fcMRI of the entire brain during rest. We placed a seed voxel within the posterior insula, a region where we previously observed elevated glutamate in chronic pain patients, and we assessed connectivity of this structure to the DMN before and after pregabalin and placebo. Interestingly, we found that during pregabalin treatment, but not placebo, patients displayed decreased insula connectivity to the inferior parietal lobule (IPL; a DMN region), which was paralleled by reductions in clinical pain: patients with greater reductions in insula-DMN connectivity displayed greater analgesia. *These findings are relevant to the proposed study because*

*they demonstrate that we can measure changes in brain networks during pharmacologic treatment and these changes are related to analgesic drug action.*

[figure not shown]

Figure above shows that change in connectivity between the posterior insula and IPL correlates with change in spontaneous clinical pain. We acknowledge that network perturbation by nitrous oxide may involve other brain regions and networks.

## OBJECTIVE

The *objective of this study* is to identify the network transformations that account for the dose-dependent analgesic and sedative-hypnotic effects of the non-GABAergic anesthetic, nitrous oxide. Our *hypothesis* is that analgesic doses of nitrous oxide increase network efficiency and disrupt normal pain processing, while higher doses significantly reduce efficiency and disrupt normal conscious processing. Our *approach* is to administer two dosing levels of nitrous oxide during the acquisition of fMRI and EEG. To differentiate analgesic action of nitrous oxide from other processes, we will compare changes in brain response to noxious pressure stimuli. Our approach is *innovative* in that no study to date has acquired fMRI or EEG data to assess non-GABAergic anesthetics or to assess the relationship between analgesia and anesthesia. The *rationale* for this study is that, once completed, we will have established a detailed understanding of the therapeutic effects (analgesia and anesthesia) of a unique and understudied class of anesthetic drugs. Our *expectation* is that the knowledge derived from this study will have a positive impact by filling in a major gap in our understanding of anesthetic mechanisms and will potentially facilitate a generalized framework for anesthetic-induced unconsciousness. Furthermore, the study will provide a sophisticated network-level understanding of the relationship between the neural states of analgesia and anesthesia.

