*Exclusion criteria* include: history of obstructive sleep apnea, history of difficult airway with previous anesthetics, gastroesophageal reflux, hypertension or other cardiovascular abnormalities, pulmonary hypertension, history of drug use, history of chronic alcohol abuse, history of pain disorders, history of depression, psychosis or bipolar disorder, history of seizures or other neurologic disorders, history of methylenetetrahydrofolate reductase deficiency (a contraindication for nitrous oxide), history of known hypersensitivity to midazolam, Zofran, labetalol or glycopyrrolate, pregnant and / or nursing mothers, contraindications to the neuroimaging methods used (i.e. metal implants), tattoos in the head/neck region (all other tattoos may be subject to study exclusion by investigators), and any impairment, activity, or situation – as determined by the study coordinator or primary investigators – that would prevent satisfactory completion of the study protocol.

*Power analysis:* We calculated power using data from fMRI analyses. Based on an effect size (Cohen's *d*) derived from preliminary data, 22 participants are required for a 90% power to detect a statistically significant reduction in average path length (reflecting network efficiency). In case of drop out across, we will continue to recruit until we have 22 volunteers with completed data sets.

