### **Consent/Pre-Scan Visit**

The study coordinator will determine whether the volunteer meets inclusion and does not meet exclusion criteria prior to consent. Following consent, each volunteer will complete a resting state questionnaire and QST familiarization/training during EEG acquisition. MR-compatible EEG cap and electrodes will be affixed to the participant's scalp to monitor brain activity during QST training. QST will consist of a constant pressure applied to the lower leg and/or visual stimulus outside of the scanner. Following each stimulus, participants will rate the pain intensity (0 = "no pain, 100 = "worst pain imaginable") and pain unpleasantness (0 = "neutral", 100 = "extremely unpleasant"). Participants will be

asked to complete another resting state questionnaire following training on simultaneous visual stimulus and pressure cuff. During this visit, participants will also be seen briefly by an anesthesiologist for an airway assessment to check for eligible Mallampati 1 or 2 airways.

Scanning Visit

Simultaneous Functional Magnetic Resonance Imaging/Electroencephalogram (fMRI/EEG)

Each volunteer will participate in one scanning visit in which simultaneous fMRI/EEG data will be collected wherein they receive placebo (20 minutes) followed by inhaled nitrous oxide at analgesic levels (35% inhaled concentration) over 40 minutes, then a nitrous oxide dose consistent with anesthetic-induced unconsciousness (70%) for 15 minutes [See Figure 1];

[figure not shown]

Figure 1. Study design schematic

Upon arrival, participants will complete baseline questionnaires (Part 1a). Prior to drug exposure, volunteers will be given an altered states of consciousness (ASC) questionnaire followed by a baseline resting state fMRI scan. During the placebo period, fMRI data will be acquired during additional tasks: visual stimulation task, evoked pressure pain applied to the lower leg induced by a cuff/automated tourniquet, and a combination visual stimulation and pressure pain cuff task. These scans will be repeated during both analgesic and anesthetic doses of nitrous oxide. End-tidal nitrous oxide concentrations will be assessed by standard gas analyzers during spontaneous ventilation through a secured face mask with tight seal.

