
### Network Analysis

In terms of network properties to be analyzed, the **degree** is the number of connections a node (in this case, a given brain region) has, while the **modularity** is a measure of the extent to which the connected regions form individual functional modules. We will first investigate the characteristic modules

corresponding to different states, then quantify the modularity of the networks. High-degree **hubs** facilitate “shortcuts” of network information transmission (much like a hub airport facilitates travel shortcuts) and are identified with the measures of *centrality* in a network. The centrality of a node measures its relative ability to integrate information globally within a brain network. We will assess several centrality measures (degree centrality, closeness centrality, betweenness centrality and Eigenvector centrality) to test the robustness of the hub structure. The **average path length**, which measures the mean number of steps along the shortest paths for all possible pairs of network nodes, will be used for quantifying the **global efficiency** of brain networks (since efficiency varies inversely with path length). Network measures will be compared across states (waking, analgesia, anesthesia) using a repeated measures two-way analysis of variance (ANOVA) and a post hoc Tukey multi-comparison test (behavioral state as the within-subjects factor, anesthetic agent as the between-subjects factor). A p value <0.05 will be considered significant.

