### EXPECTED OUTCOMES

Based on preliminary data, we predict that administration of *low-dose* nitrous oxide will decrease network modularity and increase network efficiency, disrupting normal pain processing. Specifically, we expect to see altered relationships of key pain structures (insula, thalamus, S1 and S2) and their connections with the DMN. We expect that, as cortical activation and disorganization increase with higher doses, nitrous oxide will increase network modularity and decrease network efficiency, disrupting conscious processing of the environment in general. *Our prior study of propofol and preliminary data with 60% nitrous oxide showing decreased efficiency and increased modularity suggest the exciting possibility that GABAergic and non-GABAergic anesthetics share common network-level mechanisms to induce unconsciousness.*

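### The two-direction efficiency hypothesis has no matching planned contrasts or decision rule, and the Tukey adjustment costs power for a claim that needs both halves

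*Combined protocol and SAP*

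**What the plan says.** The Objective states one hypothesis with two opposite halves: "analgesic doses of nitrous oxide increase network efficiency and disrupt normal pain processing, while higher doses significantly reduce efficiency". Expected Outcomes repeats it as predictions. Low dose should "decrease network modularity and increase network efficiency, disrupting normal pain processing"; higher doses should "increase network modularity and decrease network efficiency, disrupting conscious processing of the environment in general". Neither section says whether the high-dose fall is measured against waking or against the low dose.

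Both doses are given to the same participants in one scanning visit: placebo, then 35%, "then a nitrous oxide dose consistent with anesthetic-induced unconsciousness (70%) for 15 minutes".

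Network Analysis compares waking, analgesia and anesthesia by repeated measures ANOVA and "a post hoc Tukey multi-comparison test", with p<0.05 as the criterion. It names no planned contrasts, directions or rule linking the tests to the two-part hypothesis. It uses average path length to quantify global efficiency, "since efficiency varies inversely with path length".

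The power analysis under Methodology says that "22 participants are required for a 90% power to detect a statistically significant reduction in average path length". The effect size is described as coming from preliminary data, but no value, test or sidedness is given.

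**The concern.** The trial's central network question is whether the two doses move efficiency in opposite directions. Two separate weaknesses affect the answer.

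First, the adjustment does not fit this claim. Tukey protects against a false claim about any one of three pairs. If the pattern is declared only when both named contrasts succeed, a false declaration needs every false half to pass, so testing each at 5% already controls the error (the intersection-union argument). Tukey's higher threshold then only lowers the chance of confirming a true pattern.

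Second, no rule says what one significant half means. That reading would be settled after the data are seen. This gap costs no power; it is a matter of interpretation.

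The power statement addresses neither issue. A reduction in path length is a rise in efficiency, so the 90% matches the low-dose half. Nothing gives the power for the high-dose fall or for the pattern.

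**Working it through.** **Inputs from the documents.** 22 completers (dropouts replaced), 90% power, three within-subject states, p<0.05. **Not in the documents, so assumed:** d, the correlation between the two dose differences, sidedness and the high-dose reference state. The error term is also an assumption: I use a one-way within-subject model, because although Network Analysis also lists anesthetic agent as a between-subjects factor, this protocol gives only nitrous oxide.

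**1. The plan's own figure.** Without d, the 22 cannot be reproduced, only inverted. For a paired t-test, power = P(T > t₀.₉₇₅,₂₁ = 2.080), with T noncentral t on 21 df and noncentrality d√22. Power 0.90 requires d = 0.725 (0.725 × 4.690 = 3.40). One-sided 5% gives d = 0.645. The two-sided normal approximation gives (1.960 + 1.282)/4.690 = 0.691.

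**2. Thresholds.** Tukey, three states, error df (22−1)(3−1) = 42: studentized range 3.436, and 3.436/√2 = 2.43 on the t scale. Unadjusted two-sided 5%: 2.080 (paired, 21 df) or 2.018 (pooled, 42 df).

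**3. Base case.** d = 0.725 in each half with opposite signs, both against waking, equal variances and covariances (so the two differences correlate at 0.5), 200,000 simulated trials.
- Tukey: 83% for each contrast, 66.7% for both, exactly one half significant in 32.5%.
- Two paired tests, both required: 90% each, 80.1% for both. With the pooled error, 82.7% for both.
- Gain: 80.1 − 66.7 = 13.4 points, or 82.7 − 66.7 = 16.0 points.

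**4. Error of the proposed rule.** If one half has no effect, the pattern is falsely declared only if that contrast is significant in its stated direction. With two-sided 5% tests that is at most 2.5%.

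**5. Range (two-sided tests).**

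| Scenario (one change from the base case) | Both, Tukey | Both required, no penalty | Gain, points |
|---|---|---|---|
| Base case | 66.7% | 80.1% paired, 82.7% pooled | 13.4, 16.0 |
| Tukey threshold on separate paired errors | 61.7% | 80.1% paired | 18.4 |
| Correlation of differences 0 | 53.3% | 73.2% pooled, 81.1% paired | 19.9, 27.8 |
| Correlation of differences 0.75 | 75.4% | 80.0% paired, 87.5% pooled | 4.6, 12.1 |
| High-dose d = 1.0 | 81.5% | 89.4% paired | 7.9 |
| Both d = 1.0 | 97.2% | 98.8% paired | 1.6 |
| Both d = 0.5 | 15.7% | 30.6% paired | 14.9 |
| High dose judged against low dose | 82.9% | 90.0% paired, 91.3% pooled | 7.1, 8.4 |

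One-sided 5% tests would give 90.0% (paired) in the base case, but that changes the error level as well as the adjustment, so I leave it out of the range.

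**6. Why a rule is needed.** If only the low-dose effect is real (d = 0.725), at least one predicted half passes Tukey in 83.5% of trials and both pass in 0.4%. The two readings of the hypothesis would give very different conclusions.

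**The case against.** Tukey is a valid and defensible choice. The aim is to identify dose-dependent changes, the Objective also asks how analgesia relates to anesthesia, and all three pairs of states are of interest. The plan errs on the conservative side, in a mechanistic volunteer study. This stands: Tukey is not wrong, and it should stay for claims about one dose or the remaining pair. It is inefficient only for the claim that needs both halves.

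The size is also soft. No d is given, and equal d in both halves is a guess. The one preliminary nitrous oxide network result described (60%, in Expected Outcomes) is a decrease in efficiency, whereas the powered outcome is an increase, so it is unclear which effect produced 22. The high-dose reference state is open too. This also stands, which is why a range is shown. In every scenario examined the both-required rule had the higher joint power, but in some the difference is small.

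A reader might infer that the plan lets one half count as support. The documents do not say so. They are silent, and the Objective's wording joins the two halves. What can be said is that the plan does not rule it out.

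**Conclusion.** The point holds as a mismatch between the hypothesis and its test. The efficiency prediction has two directions, the test is all-pairs Tukey without planned contrasts, the reading of a one-half result is unspecified, and the stated power covers one direction.

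Under the base-case assumptions Tukey confirms both halves in about 67% of trials, against about 80% when both paired tests are required without a penalty. Over the scenarios examined the gain is about 2 to 28 points.

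Two stronger readings are not supported. The 13-point gap is not a property of the plan, because the documents fix none of d, correlation, sidedness or reference state. Nor does the plan promise 90% for the pattern; it attaches that figure only to a reduction in path length. The calculation also covers only the efficiency part of the hypothesis, not the disruption of pain or conscious processing.

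**What to change.** In Network Analysis, for average path length/global efficiency:

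- Pre-specify two paired contrasts with directions: 35% versus waking (efficiency up), and 70% versus a named reference state (efficiency down). The sponsor should confirm whether that reference is waking or the low dose.
- Declare the efficiency part of the hypothesis supported only if both have two-sided p<0.05 in the stated directions, without the Tukey adjustment.
- Keep Tukey for claims about a single dose and for the remaining pair.
- In the power analysis, state that the 90% covers only a reduction in path length. Give d and its source, and put the joint probability, with its assumptions and range, beside the 90%.

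This needs no more participants, scans or procedures. The costs are a little more analysis text, a one-half result that no longer counts as support for the pattern, and a stated figure for the joint efficiency pattern below 90% (about 80% in the base case).

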### Visual Stimulation Task

During the visual stimulation, participations will be undergoing a 3-minute period of dynamic visual stimulation tasks which consists of alternating 20 second blocks of flashing (8 Hz frequency) blue-yellow annulus checkerboard and a static fixation cross. The checkboard will be presented at a fixed illumination level in within the range of 4.5 to 76 lux. Following stimulation, participants will be asked to rate the intensity and unpleasantness of the stimulus on a 100-point numerical rating scale.

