## STATISTICAL ANALYSIS

### Functional connectivity magnetic resonance imaging (fcMRI)

fcMRI will be performed as described in our previous publications. During fcMRI, participants will either be at rest or receiving a pain stimulus via a pressure cuff applied to the left lower leg evoking tonic pressure with pain of 40 on a 100 point numerical rating scale (0=no pain; 100=worst pain imaginable). This sustained pain is relevant to deep musculoskeletal clinical pain and can be applied for long durations (i.e. minutes) without tissue damage. Data will be corrected for physiological effects such as cardio-respiratory fluctuations that are known to influence fcMRI estimation. Resting connectivity network analysis will be performed using the FSL (FMRIB's Software Library, [www.fmrib.ox.ac.uk/fsl](http://www.fmrib.ox.ac.uk/fsl)) software package. All data will be corrected for motion artifacts, smoothed (FWHM 5 mm), and high-pass temporal filtered ( $f = 0.006\text{Hz}$ ). ICA Approach. The within- and between-subject resting fMRI data analysis will be performed using ICA through Multivariate Exploratory Linear Optimized Decomposition into Independent Components (MELODIC, an FSL tool) and a previously validated dual regression approach. We will apply probabilistic ICA to identify global, independent patterns of functional connectivity existent in the entire subject population. The number of independent components will be limited to 25 to reduce subcomponents. Networks of interest will be selected and the spatial independent component maps identified from the population data will be used as a spatial regressor in a general linear model of the subject's resting fcMRI data. This will allow us to estimate subject-specific spatial maps for each component. These maps will then be passed up to group analysis. Seed-voxel Approach: We will evaluate functional connectivity using seed-voxels from brain regions previously shown to be involved in consciousness or pain. The average time course in these regions will be used as regressors in a whole brain general linear model to find other brain regions also correlated with the seed region. A whole brain general linear model will be performed using the seed time course, averaged over a 3 mm radius sphere, as the regressor of interest. The resulting single subject maps will be normalized to standard space and passed up to group analyses. fcMRI group analyses: Nitrous oxide effects on brain connectivity will be estimated using a factorial model with treatment (nitrous versus placebo) and time (pre versus post) as factors. All statistical maps will be corrected for multiple comparisons on the cluster level  $p < 0.05$ , derived from an uncorrected  $p < 0.001$  on the voxel level.

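### Comparing responses to noxious pressure cannot by itself separate analgesia from a general loss of sensory response, and no analysis is specified for the visual and combined runs that could help

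*Combined protocol and SAP*

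**What the plan says.** The Objective gives one means of isolating the analgesic effect: "To differentiate analgesic action of nitrous oxide from other processes, we will compare changes in brain response to noxious pressure stimuli." It names no non-noxious comparator. Expected Outcomes then predicts that the low dose will disrupt pain processing, with altered relationships between the insula, thalamus, S1 and S2 and the default mode network (DMN).

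The Scanning Visit text lists the placebo-period tasks as "visual stimulation task, evoked pressure pain applied to the lower leg induced by a cuff/automated tourniquet, and a combination visual stimulation and pressure pain cuff", and adds: "These scans will be repeated during both analgesic and anesthetic doses of nitrous oxide." The Visual Stimulation Task section describes a 3-minute run of "alternating 20 second blocks of flashing (8 Hz frequency) blue-yellow annulus checkerboard and a static fixation cross", at a fixed illumination level, and continues: "Following stimulation, participants will be asked to rate the intensity and unpleasantness of the stimulus on a 100-point numerical rating scale." The Questionnaire section confirms that ratings are taken for both cuff and visual scans.

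The fcMRI part of the Statistical Analysis says: "During fcMRI, participants will either be at rest or receiving a pain stimulus via a pressure cuff applied to the left lower leg." Its group model has treatment and time as factors. The Network Analysis section compares measures across waking, analgesia and anesthesia, with behavioral state and anesthetic agent as factors. It does not say which runs supply the data.

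**The concern.** The Objective promises to tell analgesia apart from other processes, and the same section names sedative-hypnotic effects as part of what the drug does. A drug that makes volunteers drowsy or inattentive would weaken the response to a painful cuff and also to a flashing checkerboard. Looking only at the cuff response cannot show which has happened.

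The trial collects a non-noxious run in every state, so some evidence on this question will exist, but nothing says how it will be used. If the comparison is added after the data are seen, it will carry much less weight. What is at stake is the pain-specific reading of the 35% effect. The two Specific Aims, which concern dose-dependent network and feedback-connectivity changes, do not depend on it.

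**Working it through.** **1. Runs collected against runs analysed.**

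| Run | Collected (Scanning Visit) | Named in fcMRI analysis | Named in Network Analysis |
|---|---|---|---|
| Rest | yes | yes | input runs not stated |
| Cuff | yes | yes | input runs not stated |
| Visual | yes | no | input runs not stated |
| Visual plus cuff | yes | no | input runs not stated |

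Factors in the two models are treatment, time, state and agent. None is stimulus type. A cuff-versus-rest contrast is not specified either. Rest runs can show a shift in baseline connectivity, but they cannot show a general loss of response to sensory input. The cuff and visual ratings have no stated analysis.

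**2. The plan's own figure.** The Power analysis gives 22 participants for 90% power on average path length. It does not give d, the test or the sidedness, so 22 cannot be reproduced forward. Back-solving a paired t test at 5% with n = 22 and 90% power gives d = 0.725 two-sided (0.645 one-sided). This d belongs to path length. Below it serves only as a reference size for a cuff response.

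**3. Noxious-only test under purely general depression (illustrative).** Power = P(|T| > t(0.975, 21)), with T noncentral t on 21 df and noncentrality d√22.

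| General effect d | d√22 | Probability of significance |
|---|---|---|
| 0.2 | 0.94 | 0.15 |
| 0.3 | 1.41 | 0.27 |
| 0.5 | 2.35 | 0.61 |
| 0.725 | 3.40 | 0.90 |

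**4. The cuff-versus-visual contrast.** Let the cuff and visual changes (35% versus placebo, each relative to rest) have equal SDs and correlation rho. The standardised contrast is (d_cuff − d_visual) / √(2(1 − rho)).

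- *Equal blunting:* the numerator is zero, so the rejection rate is the 5% test level. Simulation of 20,000 trials gave 4.8% to 5.0% for rho 0.3 to 0.7.
- *Wholly pain-specific effect:* d_cuff = 0.725, d_visual = 0.
- *Unequal differences:* d_cuff = 0.725, d_visual half of that, so the numerator is 0.3625.

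| rho | Standardised contrast, numerator 0.725 | Probability of significance | Standardised contrast, numerator 0.3625 | Probability of significance |
|---|---|---|---|---|
| 0 | 0.513 | 63% | 0.256 | 21% |
| 0.3 | 0.613 | 78% | 0.306 | 28% |
| 0.5 | 0.725 | 90% | 0.363 | 37% |
| 0.7 | 0.936 | 99% | 0.468 | 55% |

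The last column has two readings. It is the power when half of the cuff effect is pain-specific. It is also the false-positive rate when depression is wholly general but the visual change is half the cuff change.

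**5. How well the runs match.** At TR 2 s, the 3-minute visual run gives 180/2 = 90 volumes and the 6-minute cuff run gives 360/2 = 180. The visual run alternates 20-second blocks, so only about half of it carries the stimulus. The cuff is continuous. Cuff pressure is calibrated to each volunteer's pain, whereas illumination is fixed. Trimming the cuff run to 90 volumes equalises length but not design.

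**The case against.** The strongest reply is that the documents claim less than a critic might read into them, and several parts of that reply stand.

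- A reader might infer that the visual and combined runs enter no analysis at all. The Network Analysis section does not name its input runs, so the documents support only the statement that no analysis is specified for them.
- A reader might infer that general depression would be reported as analgesia. No section says that a significant cuff change will be given that label, and Expected Outcomes predicts a regional pattern and not merely a weaker response. What holds is that the two explanations could not be told apart.
- A reader might call the visual task the trial's built-in control. The documents never do. That use is a reasonable inference, but the match to tonic cuff pain is imperfect.
- A reader might set 90% against 5% as the gain from the contrast. The 5% follows from assuming equal blunting. With a visual change half the cuff change, the contrast would be significant in 21% to 55% of trials with no pain-specific effect. The planned fcMRI analysis is also a cluster-corrected whole-brain map and not a single paired t test.
- A rule that treats a non-significant contrast as proof of a general effect would be unsound. A wholly pain-specific d of 0.725 is missed in 100 − 63 = 37% of trials at rho 0 and 100 − 78 = 22% at rho 0.3.

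These points limit the size of the claim and the weight the contrast can bear. They do not supply the missing comparison. The Objective still rests the separation on noxious stimuli, and no stimulus-type contrast is written anywhere.

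**Conclusion.** The point holds as a gap between a stated objective and the analysis meant to meet it. As written, the plan cannot distinguish analgesia at 35% from a general reduction in response to stimulation, although it collects data that bear on the question. This should be corrected. It does not undermine the dose-dependent aims.

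The structural finding rests on the text alone. The sizes are illustrative, because neither the effect on the cuff response nor rho is given: about 15% to 90% significance for a noxious-only test under general depression of d = 0.2 to 0.725, and about 63% to 99% power for the contrast if an effect of 0.725 is wholly pain-specific. They assume 22 completers, equal SDs and a two-sided 5% paired test on a single measure.

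**What to change.** Add to the Statistical Analysis:

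1. One pre-specified contrast at 35% versus placebo: (cuff minus rest) minus (visual minus rest), on one named connectivity measure. Insula-DMN connectivity would fit Expected Outcomes. If both terms use the same rest run, rest cancels and the contrast is the change in cuff minus visual; rest is still needed for item 3.
2. The same cuff-versus-visual contrast for the intensity and unpleasantness ratings. Name one scale: the task sections give a 100-point numerical scale and the Questionnaire section gives the Gracely Box Scale.
3. Separate reporting of the cuff and visual changes, with the contrast and its confidence interval.
4. A wording rule: describe the 35% effect as pain-specific only if the contrast supports it; otherwise report 'specificity not shown', and do not report a general effect.
5. Run-length-matched data (90 volumes) as a sensitivity analysis, with a statement that the block-design, fixed-illumination visual task is an imperfect match for tonic, pain-calibrated pressure. The contrast is supporting evidence and not proof.
6. Descriptive reporting at 70%, where the volunteer may not see the stimulus.
7. A sentence on how the combined runs will be used, or that they are exploratory.

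The cost is SAP wording and one additional contrast on scans and ratings already planned, with no new volunteers or exposure. The drawback is limited precision, so the power of the contrast should be stated across a range of rho. The present power statement covers only average path length.
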